# 2.3 POPULATIONS FOR ANALYSES

Populations that will be analyzed include the following:

- Intention-to-Treat (ITT) Analysis Dataset (i.e., all enrolled participants)
- Per-Protocol Analysis Dataset: defines enrolled patients for whom no protocol deviations were noted
- Full Cohort Dataset: includes the ITT population plus the Run-in patients

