Sample Size Considerations	There is no statistically based sample size for this study which is being conducted to obtain confirmatory evidence to support the safety of using the ENVUE System as an adjunct to current placement practices for nasoenteral feeding tubes. Forty (40) to Fifty (50) subjects (includes run-in subjects) completing the Procedure Visit (NasoEnteral Tube placement procedure) will provide evidence that the NET tube guidance system does not present new or different safety issues as compared to the predicate (confirmatory study). If less than 35 patients will complete the Follow-up Visit (confirmation of tube tip anatomical location), an enrollment of another 5 patients will be considered.				
SCHEDULED VISITS	This study is an acute safety assessment of the ENVUE System covering the guidance functionality of the System.  Screening The screening visit will occur at time zero and will assess eligibility for the study and				
	obtain informed consent.  Procedure  The study procedure may occur within two days of screening. Informed consent will be affirmed and the patient will be considered enrolled.				
	Final Follow Up The final follow-up visit will occur 20-48 hours following the procedure.				
Inclusion Criteria	
 
Patients must be ≥21 years of age
 
Patients must require placement of a nasoenteral feeding tube
 
Patients have an endotracheal tube, OR         
 
Do not have an endotracheal tube but are sedated and/or classified as obtunded¹ at the time of placement
 
 
 
Patients or legal authorized representative must be able to understand and
 
				
	adhere to all protocol procedures and be willing and able to provide written informed consent 				

Obtundation level evaluation is based on Glasgow-Coma scale with a score of between 9 and 12. Sedation level is based on Richmond Agitation-Sedation Scale (RASS) score of -2 or less.
Consent may be provided by patient's legal authorized representative.

 NUTRI-002
 Version 1.3

 July 11, 2018

	Patients must not have a history of:				
EXCLUSION CRITERIA	
 
Esophageal varices or ulcers
 
				
	
 
Upper airway obstruction
 
				
	
 
Upper GI stenosis or obstruction
 
				
	
 
Trauma involving sinuses, nares face or neck that would prevent NG
 
				
	or oral tube insertion				
	
 
Deformities of the sinus cavities and/or skull base
 
				

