# **Enrollment**

- Affirmation of informed consent and enrollment (Only if screening visit is independent of procedure visit)
- ENvizion nasoenteral feeding tubes will be placed in 5 run-in subjects prior to enrollment of the remaining subjects
- •Enroll the rest of the subjects

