### 2.2 SAMPLE SIZE DETERMINATION

This feasibility trial will include forty (40) to fifty (50) patients completing the Procedure Visit (NasoEnteral Tube placement) and at least five operators. ENvizion nasoenteral feeding tubes will be placed in 5 run-in subjects prior to enrollment of the remaining subjects. All enrolled subjects (run-in subjects and trial subjects) will be included in the final analysis. Patients or patients' LAR who chose not to participate after informed consent but prior to procedure, and patients who because of system malfunction or because of undiscovered or unreported physical reasons (e.g. deteriorating health, anatomical anomalies, mechanical obstruction, etc.) cannot complete the Procedure Visit (NasoEnteral Tube placement) will be considered Screen Failures, not be considered in the total patient count, but will be reported in the ITT dataset as defined below. If less than 35 patients will complete the Follow-up Visit (confirmation of tube tip anatomical location), an enrollment of another 5 patients will be considered.

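### ITT already contains the run-ins that Full Cohort adds, no analysis set is named primary, and no rule says how uncompleted placements count towards procedure success

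*Combined protocol and SAP*

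**What the plan says.** **Run-ins.** Section 2.2 and the synopsis (Number of Subjects and Sites) treat run-ins as enrolled: "All enrolled subjects (run-in subjects and trial subjects) will be included in the final analysis". The synopsis (Sample Size Considerations) places them inside the recruitment target: "Forty (40) to Fifty (50) subjects (includes run-in subjects) completing the Procedure Visit". The schema in 1.2 is consistent with this: after the 5 run-in placements, its next step is "Enroll the rest of the subjects".

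**Analysis sets.** Section 2.3 lists "Intention-to-Treat (ITT) Analysis Dataset (i.e., all enrolled participants"), a Per-Protocol set of enrolled patients without deviations, and "Full Cohort Dataset: includes the ITT population plus the Run-in patients". Section 2.4 calculates procedure success in every set and ranks none of them.

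**Enrolment.** The synopsis (Scheduled Visits) fixes the moment at the Procedure visit: "Informed consent will be affirmed and the patient will be considered enrolled".

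**Patients who do not complete placement.** Section 2.2 puts two groups under one label. The first is patients "who chose not to participate after informed consent but prior to procedure". The second is patients in whom placement could not be completed because of system malfunction or a physical reason not known beforehand. Both groups "will be considered Screen Failures, not be considered in the total patient count, but will be reported in the ITT dataset as defined below". The synopsis also keeps screen failures outside the 40 to 50.

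**The concern.** Three things are left open.

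1. **What ITT means.** If run-ins are enrolled and ITT is everyone enrolled, adding the run-ins to ITT adds nobody. The likely intent was an ITT set without run-ins, but the text does not say so. Two analysts could report different rates under the same label.
2. **Which rate leads.** Procedure success is the primary endpoint, but none of the three sets is designated for it. The commitment to include all enrolled subjects in the final analysis says who is analysed, not which rate is the headline.
3. **How an uncompleted placement is scored.** A patient whose placement fails at the Procedure visit is already enrolled under the synopsis, so Screen Failure is the wrong label. The plan does not say whether that patient is not successful, missing or only listed. System malfunction matters most, because it is a failure of the device under study. If the total patient count served as the denominator, such failures would leave the success rate.

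**Working it through.** **Is there a figure to reproduce?** No. The synopsis says the sample size has no statistical basis, and section 2.1 states no formal hypothesis. The check therefore compares the set definitions and shows how far the rate can move. The documents give no expected rate, so every failure count below is an assumption.

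**Inputs from the documents.** 40 to 50 patients completing the Procedure visit (2.2 and synopsis), and 5 run-ins (2.2) within that number (synopsis, Sample Size Considerations). The possible extra 5 patients are left out.

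**Step 1: set sizes, completers only.**

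| Reading | ITT | Full Cohort |
|---|---|---|
| ITT as written (run-ins included) | 40 to 50 | 40 to 50, the same patients |
| ITT meant to exclude run-ins | 35 to 45 | 40 to 50 |

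The rate with run-ins is reported under either reading. What changes is the meaning of ITT.

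**Step 2: effect of the run-ins on the ITT rate.** Take N = 40 with k failures (k up to 5). The rate with run-ins is (40 − k)/40.

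- No failure in a run-in: the rate without run-ins is (35 − k)/35, and the difference (without minus with) is −k/280, or −0.36k percentage points.
- All failures in run-ins: the rate without run-ins is 35/35, and the difference is k/40, or +2.5k points.

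For k = 1 the difference runs from −0.4 to +2.5 points, and for k = 4 from −1.4 to +10.0. The upper ends require every failure to fall in a run-in. With one failure, and exact (Clopper-Pearson) 95% intervals:

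- Run-ins included: 39/40 = 97.5% (86.8 to 99.9).
- Run-ins excluded, failure in a run-in: 35/35 = 100% (90.0 to 100).
- Run-ins excluded, failure in another patient: 34/35 = 97.1% (85.1 to 99.9).

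**Step 3: effect of uncompleted placements.** Take two failures among the completers and m further enrolled patients whose placement could not be completed. If those m are only listed, or the total patient count is the denominator, the rate is 38/40. If they count as not successful, it is 38/(40 + m).

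| Completers | m | Rate | Exact 95% CI |
|---|---|---|---|
| 40 | 0 | 38/40 = 95.0% | 83.1 to 99.4 |
| 40 | 1 | 38/41 = 92.7% | 80.1 to 98.5 |
| 40 | 2 | 38/42 = 90.5% | 77.4 to 97.3 |
| 40 | 5 | 38/45 = 84.4% | 70.5 to 93.5 |
| 50 | 0 | 48/50 = 96.0% | 86.3 to 99.5 |
| 50 | 2 | 48/52 = 92.3% | 81.5 to 97.9 |

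Two such patients therefore lower the rate by 95.0 − 90.5 = 4.5 points with 40 completers, and by 96.0 − 92.3 = 3.7 points with 50.

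**The case against.** The strongest reply is that the plan largely handles uncompleted placements already. Section 2.2 sends these patients to ITT, section 2.4 calculates success in ITT, and the endpoint asks whether the tube can be correctly placed. A patient in whom it could not be placed does not meet that definition. Leaving these patients out of the patient count can be read as a recruitment rule, since it stands in the sample size section. This reply mostly stands. A reader might infer that the plan removes device failures from the primary success rate, and the documents do not support that. It happens only if reporting in ITT means listing, or if the total patient count is used as the denominator. What remains is that neither reading is excluded and no scoring rule is written.

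A reader might also infer that every patient who withdraws before the procedure conflicts with the ITT definition. That goes too far. Consent is affirmed and enrolment occurs at the Procedure visit, so a patient can be enrolled and then withdraw before insertion. The conflict exists only for those who withdraw before enrolment.

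Nor can a reader infer that run-ins might vanish from the results, because section 2.2 commits to including them.

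Finally, the trial is descriptive, with no hypothesis or threshold. That is correct and limits the weight of the point. But a descriptive result rests on its numerator and denominator, and the synopsis intends it as confirmatory safety evidence relative to the predicate.

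**Conclusion.** The point holds and should be fixed. The overlap between ITT and Full Cohort and the absence of a primary set follow directly from the text. So does the conflict between enrolling patients at the Procedure visit and calling those who fail placement there Screen Failures. The scoring of uncompleted placements is a missing rule. The plan's wording leans towards non-success, so this is not a stated exclusion of failures.

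The consequence is limited to the reported rate and its label; no error rate or power is affected. In the illustrations, one failure moves ITT by −0.4 to +2.5 points depending on whether run-ins are in, and two uncompleted placements lower the rate by about 4 to 5 points. These sizes rest wholly on assumed counts and are not bounds.

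**What to change.** - **Section 2.3:** define ITT as all patients enrolled at the Procedure visit, run-ins included, and name it the primary set for procedure success. Replace Full Cohort with a supportive set that excludes the 5 run-ins. Per-Protocol can stay as it is.
- **Section 2.2 and the matching synopsis line (Number of Subjects and Sites):** state that enrolled patients in whom use of the system or tube placement was started but could not be completed are not Screen Failures, and count as not successful in the primary denominator. Include system malfunction before or during insertion. Keep 40 to 50 completers as the recruitment target.
- **Screen Failures:** restrict the term to patients who leave before enrolment, and list them outside ITT.
- **Enrolled but no attempt, for reasons unrelated to the device** (such as withdrawal or worsening health): keep these patients in ITT, list them by reason, and also show the rate among attempted placements, so that device failures can be told apart from other reasons.

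The cost is a few lines of rewording in 2.2, 2.3 and the synopsis, with no extra patients or data. The downside is that the headline rate may be slightly less favourable, because uncompleted placements count against it.

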### 2.4 STATISTICAL ANALYSES

The procedure success will be calculated for all populations. Additional descriptive statistics will be presented as appropriate using means, standard deviations, medians and ranges for the continuous variables and as counts and percentages for categorical variables.

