# PROTOCOL SUMMARY

1.1 SYNOPSIS			
STUDY TITLE	A Feasibilty Study to Evaluate the Clinical Safety of ENvizion™ Nasoenteral Feeding Tube Placement using the ENvizion™ ENVUE System in Patients.		
PROTOCOL NUMBER	NUTRI-002		
DEVICE DESCRIPTION	The ENvizion™ ENVUE™ System is designed to aid qualified operators in the placement of the ENvizion™ NasoEnteral Tube™ of 10 Fr to 12 Fr into the stomach or small intestine of patients requiring enteral feeding. The ENVUE System is intended as an adjunct to current placement practices for assisting clinical practitioners who place feeding tubes in adult patients.		
	The ENvizion™ NasoEnteral Tube has been specifically designed for use with the ENVUE™ System and is intended for placement in the stomach or small intestine. It is intended for use in adult patients who require intermittent or continuous feedings via the nasogastric or nasoenteric route.		
STUDY OBJECTIVES	The objective of this study is to assess the safety of the ENVUE System as an adjunct to current practices for placement of nasoenteral feeding tubes.		
STUDY DESIGN	The study is a prospective, single center, non-randomized clinical trial in patients that require placement of a nasoenteral feeding tube as a result of their current medical condition.		
NUMBER OF SUBJECTS AND SITES	Up to fifty (50) subjects and at least forty (40) will complete the Procedure Visit (NasoEnteral Tube placement procedure, section 1.3) at a single center by at least five operators. This number (40-50 subjects) does not include screen failures. Envizion nasoenteral feeding tubes will be placed in 5 run-in subjects prior to enrollment of the remaining subjects. All enrolled subjects (run-in subjects and trial subjects) will be included in the final analysis.		
DURATION OF PARTICIPATION/STUDY	Each patient's individual participation will last approximately 20-48 hours.  It is expected the entire study will take approximately two (2) months to complete.		
STUDY ENDPOINTS	Primary Endpoint:		
	Procedure success: Nasoenteral tube (NET) can be placed in the correct anatomical position without occurrence of guidance-related adverse events.		

Version 1.3 NUTRI-002 July 11, 2018

	Additional Assessments:				
	Procedure Metric s: Number of placement attempts required				
	Safety: Adverse Events				

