	
 
Esophageal cancer or neoplasm
 
				
	Patients must not have a significant concomitant illness that would adversely				
	affect their participation in the study				
	Female patients who are pregnant or lactating				
STATISTICAL ANALYSIS	All data will be reported using summary statistics.				
OTHER CONSIDERATIONS	No core lab will be charted for this study; thus, judgements regarding placement will be based on the investigator's assessment of X-Ray images. Assessments of relatedness of any noted adverse events to the study device will be adjudicated by a Clinical Events Committee (CEC). No DSMB will be chartered for this study based on the well-understood safety profile.				
US REGULATORY STATUS	The ENVUE System is considered a non-significant risk investigational device in the United States.				

Version 1.3 NUTRI-002 July 11, 2018

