# 2 STATISTICAL CONSIDERATIONS

# 2.1 STATISTICAL HYPOTHESES

There is no formal statistical hypothesis for the primary endpoint of this feasibility trial. The primary endpoint is defined as procedure success, e.g., NET tube can be placed in the correct anatomical position without occurrence of guidance-related adverse events.

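### Procedure success is planned as summary statistics only, with no confidence interval and no breakdown into correct position and freedom from guidance-related adverse events

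*Combined protocol and SAP*

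**What the plan says.** The synopsis gives one objective: "The objective of this study is to assess the safety of the ENVUE System" as an adjunct to current placement practice. The primary endpoint is procedure success, which section 2.1 defines as "NET tube can be placed in the correct anatomical position without occurrence of guidance-related adverse events". It is therefore a composite of position and freedom from a class of adverse event.

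The analysis text is short. Section 2.4 says "The procedure success will be calculated for all populations", and section 2.3 defines three of these. Other descriptive statistics are to be added where appropriate, with categorical variables shown "as counts and percentages for categorical variables". The synopsis adds: "All data will be reported using summary statistics".

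Adverse events are a separate additional assessment in the synopsis, collected at the procedure and follow-up visits (Table 1). A Clinical Events Committee adjudicates whether events are related to the study device (synopsis, Other Considerations).

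On size, section 2.2 says "This feasibility trial will include forty (40) to fifty (50) patients completing the Procedure Visit". Section 2.1 says "There is no formal statistical hypothesis for the primary endpoint of this feasibility trial". The synopsis says the sample size has no statistical basis. It also says the study is meant to be confirmatory, showing that the guidance system raises no safety problem beyond those of the predicate.

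**The concern.** Two things are missing from the planned analysis of the primary endpoint.

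The first is a measure of precision. With 40 to 50 patients, a high success rate, or an absence of guidance-related events, is compatible with a wide range of true rates. There is no hypothesis, margin or comparator arm, so an interval is the simplest way to show how far the data support the stated safety conclusion.

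The second is the component breakdown. A misplaced tube with no adverse event and a correctly placed tube with a guidance-related adverse event each count as one failure. The same success rate can therefore go with very different rates of guidance-related events, and those events bear directly on the objective. The separate adverse event summary does not clearly fill this gap. No per-patient proportion with a guidance-related event is specified, the committee's stated remit is relatedness to the device rather than to guidance, and nothing links events to procedure failures.

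**Working it through.** **Figure to reproduce.** None. The plan states no rate, precision target, alpha or power.

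**Inputs.** From section 2.2: n = 40 and n = 50, the planned range of patients completing the procedure visit. Assumed, because the documents give no value: a two-sided 95% level and the counts of successes and events below.

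**Formula.** For x out of n, the exact (Clopper-Pearson) limits are

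- lower = 0.025 quantile of Beta(x, n − x + 1), or 0 if x = 0;
- upper = 0.975 quantile of Beta(x + 1, n − x), or 1 if x = n.

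For x = 0 the upper limit reduces to 1 − 0.025^(1/n).

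**Step 1: precision of the composite.**

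| Assumed result | Rate | Exact 95% interval |
|---|---|---|
| 40/40 | 100% | 91.2 to 100 |
| 38/40 | 95% | 83.1 to 99.4 |
| 36/40 | 90% | 76.3 to 97.2 |
| 50/50 | 100% | 92.9 to 100 |
| 48/50 | 96% | 86.3 to 99.5 |
| 45/50 | 90% | 78.2 to 96.7 |

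For 36/40 the limits come from Beta(36, 5) and Beta(37, 4). At 90% success the interval is 97.2 − 76.3 = 20.9 points wide with 40 patients and 96.7 − 78.2 = 18.5 points wide with 50.

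**Step 2: what one success rate can contain.** Take 36/40, which has 4 failures. The number of patients with a guidance-related adverse event can be anything from 0 to 4.

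- All 4 failures are misplacements without such an event: 0/40 = 0%, interval 0 to 8.8%.
- All 4 failures have such an event: 4/40 = 10%, interval 2.8 to 23.7%.

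The reported success rate is 90% in both cases. With 45/50 the same extremes are 0/50 (0 to 7.1%) and 5/50 = 10% (3.3 to 21.8%).

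**Step 3: what zero events would show.**

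- n = 40: 1 − 0.025^(1/40) = 8.8%.
- n = 50: 1 − 0.025^(1/50) = 7.1%.

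If the true rate were 2% (assumed), the chance of seeing at least one affected patient would be 1 − 0.98^40 = 55% with 40 patients and 1 − 0.98^50 = 64% with 50. An event-free study would therefore be unsurprising even if such events do occur.

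**The case against.** The strongest reply is that this is a declared feasibility study. It has no hypothesis, no statistical sample size and no decision rule that an interval could change. Counts are planned for categorical variables, so any reader given n/N can work out the interval. Adverse events are collected at two visits and reviewed by a committee, and section 2.4 leaves room for further descriptive statistics. Classifying a patient on the composite already requires both parts to be determined. What is missing is a planned table, not data.

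Much of this stands, and it rules out several stronger readings.

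- A reader might infer that the primary result will be a single bare percentage. It will not: success is calculated in three datasets, and counts are planned. Precision is unstated, not concealed.
- A reader might infer that harm will go unreported. The separate adverse event assessment contradicts that.
- A reader might take the failures to be either injuries or harmless misplacements. The documents use neither term. They attach no severity to guidance-related events, and a misplaced tube is itself a failure of the guidance function under study.
- A reader might infer that a hypothesis or a powered sample size is required. The plan openly declares that it has neither, and this point asks for neither.

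The reply does not answer two things. Counts for the composite give its interval but cannot give the component split. And the synopsis claims confirmatory evidence of safety relative to the predicate, which goes beyond feasibility and makes a stated measure of precision useful even without a test.

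**Conclusion.** The point holds as a gap in the specified analysis: no interval and no component breakdown are planned for procedure success. The breakdown is the stronger half, because a reader could not reconstruct it from the success rate.

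On size, a 90% success rate would carry an interval about 18 to 21 points wide and could contain a guidance-related event rate of 0% or 10%. Observing no such events would still leave a true rate of about 7 to 9% within the 95% limits. These figures rest on the planned 40 to 50 patients, an assumed two-sided 95% level and assumed counts. They illustrate precision and do not predict results.

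This is a cheap improvement to reporting. The documents do not support a claim that the planned rates would be wrong or that the trial could not be interpreted.

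**What to change.** In section 2.4, add wording such as: *Procedure success will be reported as n/N with an exact (Clopper-Pearson) two-sided 95% confidence interval in each dataset. Its components, (a) correct anatomical position and (b) freedom from guidance-related adverse events, will each be reported as a per-patient proportion with the same type of interval. All procedure failures will be listed by cause.* Component (b) may equally be shown as the proportion with at least one guidance-related adverse event.

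Two details should be settled in the same edit. One is who classifies an event as guidance-related, since the committee's stated remit is relatedness to the device. The other is how patients who cannot complete placement count in each component, since section 2.2 keeps them in the ITT dataset. Three proportions in three overlapping datasets give 3 × 3 = 9 intervals, so the text should also say that they are descriptive and which dataset leads.

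The cost is a few sentences and a few lines of code, with no added patient, visit or procedure, because the endpoint already requires both components for each patient. The downside is that the reported figures will look less certain.
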